2.3 RISK/BENEFIT ASSESSMENT

2.3.1 KNOWN POTENTIAL RISKS

There is a risk of loss of PHI which will be mitigated by use of secure servers at the University of Michigan campus. The cloud that receives digital information from the inhalers is HIPAA compliant and under the control of TEVA. TEVA collaborating investigators will partner with a cross-functional internal team and principal investigator/sponsor to determine the appropriate AE/SAE reporting requirements and reporting structure.

Clinical Safety: A total of 1289 subjects were treated with PROAIR® RESPICLICK during the clinical development program. The most common adverse reactions ($\geq 1\%$ and $>$ placebo) were back pain, pain, gastroenteritis viral, sinus headache, and urinary tract infection. In a long-term study of 168 patients treated with PROAIR® RESPICLICK for up to 52 weeks (including a 12-week double-blind period), the most commonly reported adverse events $\geq 5\%$ were upper respiratory infection, nasopharyngitis, sinusitis, bronchitis, cough, oropharyngeal pain, headache, and pyrexia. In a small cumulative dose study, tremor, palpitations, and headache were the most frequently occurring ($\geq 5\%$) adverse events.

2.3.2 KNOWN POTENTIAL BENEFITS

Participants in this study will receive free asthma maintenance and rescue inhalers and access to information in the Digihaler™ app that may have a positive impact on their health behaviors.

2.3.3 ASSESSMENT OF POTENTIAL RISKS AND BENEFITS

This is a minimal risk study that will focus on real world use of approved medications with an emphasis on understanding patterns of use, inhalational parameters, and changes in these measurements during acute episodes of asthma. Patients will be encouraged to follow the clinical guidance that is provided by the treating physician.

The ProAir® Digihaler™ is a rescue/reliever agent that includes an eModule on top of the approved PROAIR® RESPICLICK inhaler. The system consists of the ProAir® Digihaler™, the App, the cloud solution, and the dashboard. The ProAir® Digihaler™ can be used with or without the additional devices (App, cloud solution, and dashboard) that are being evaluated in this study. The on-board electronics and power source in the Digihaler™ are fully integrated into the inhaler and are designed to operate for the life of the inhaler without intervention. The eModule records timestamped pre-defined events. The inclusion of the eModule has been shown to have no impact on the dose delivery compared with the approved product without the eModule (performance and functional testing on file at Teva). Furthermore, the steps to take a dose of ProAir® Digihaler™ are identical to that of the currently approved PROAIR® RESPICLICK. Therefore, it is unlikely that the inclusion of the eModule will add additional risk to the approved product. In summary, the benefit and risk assessment for ProAir® Digihaler™ is favorable following review of the outlined data.

3 OBJECTIVES AND ENDPOINTS

OBJECTIVES	ENDPOINTS	JUSTIFICATION FOR ENDPOINTS
Primary		

To determine the baseline inhalation parameters and patterns of use of both the maintenance (AirDuo®) and rescue (ProAir®) Digihaler™ in patients with severe persistent asthma who are being treated with biologics from baseline through the duration of the 12-month treatment period
	
 • Mean number of daily doses of ProAir® Digihaler™ • Mean number of daily doses of AirDuo® Digihaler™ • Median number of daily doses of ProAir® Digihaler™ • Median number of daily doses of AirDuo® Digihaler™ 	
The number of inhalations of rescue and maintenance bronchodilator use varies amongst and within patients with severe asthma and is impacted by changes in asthma control. This is a clinically meaningful measurement that is included in assessments of disease activity and control. PIF, inspiratory time and volume vary with changes in baseline asthma control and may be important in identifying acute exacerbations of asthma.
 
Maintenance therapies can impact asthma control and confound the response to biologics. In addition, the patterns of use of maintenance therapies and the potential discordance with rescue inhaler use would be important to delineate in this severe asthma population.

Secondary		

To determine the impact of variable degrees of adherence to maintenance therapy on outcomes to biologics. The Digihaler™ will allow us to collect accurate information on adherence that will be utilized to divide patients into groups and to assess asthma outcomes such as change in mean FEV1, exacerbations, oral steroid reduction, and asthma control (using the asthma control
	
 • Proportion of patients with different adherence rates. 
Tests: Summary, chi-squared test, and Tukey’s HSD test statistics of asthma outcomes by adherence group.
	
Adequate understanding of adherence is essential for guiding treatment decisions in clinical asthma care. It may impact response to biologics particularly in patients that are partial responders to targeted therapies. The degree of asthma control while on biologics may be altered by

OBJECTIVES	ENDPOINTS	JUSTIFICATION FOR ENDPOINTS

test scores over time) in patients receiving biologic therapies.
 
Definitions: Adherence rates will be defined as: high (>80% of puffs), moderate (50-80% of puffs) and low levels (<50% of puffs) of adherence to maintenance inhalers (assuming an expected baseline usage of two puffs per day).
		
non-adherence to inhaled therapies and lead to incorrect conclusion that the biologic is not effective. In addition, little is known about how patients with severe asthma utilize their inhalers once biologics are initiated and more importantly if it is safe to discontinue these therapies altogether.

To determine the impact on inhalation parameters on categorical response to biologics. Response will be categorized as non-response, partial and complete response on the basis of six factors: a 50% reduction in exacerbations, any reduction in maintenance OCS dose, change of at least 10% in FEV1, improvement of 3 points in ACT score and patient perception of global improvement in asthma.
	
 • Proportion of patients achieving non-response, partial and complete response to biologics. 
Tests: Summary, chi-squared test, and Tukey’s HSD test statistics of inhalation parameters by response group.
	
Response to biologics is heterogeneous, and it is unclear if inhalational parameters measured by the Digihaler™ are correlated with degree of response.


To determine whether inhalation measurements can serve as surrogates of standard expiratory flow measurements. Specifically, to determine the correlation between PIF with FEV1 and identify thresholds for changes in PIF that are associated with a clinically meaningful increases or decreases (10%) in lung function as measured by conventional spirometry (e.g., FEV1).
	
 • Change in Main Peak Inspiratory volume from baseline up to one year • Change in Mean Inspiratory Time from baseline up to one year • Change in mean peak inspiratory flow (PIF) from baseline up to one year • Change in mean forced expiratory volume in one second (FEV1) from baseline up to one year 
Tests: Correlation coefficients, regression equations, and regression summary statistics (e.g., R-squared,
	
FEV1 is a well-established and accepted measure of lung function in asthma. Changes in FEV1 are noted during acute episodes and clinically meaningful changes have been established. Little is known about the correlation between FEV1 and PIF and whether change in PIF could serve as a surrogate for change in FEV1.

OBJECTIVES	ENDPOINTS	JUSTIFICATION FOR ENDPOINTS
	
mean absolute error) for PIF vs. FEV1, PIF vs. FVC. Identification of change in PIF thresholds (increase and decrease thresholds) that are clinically meaningful.
 
Univariate/multivariate regression statistics between inhalation parameters and asthma outcomes such as asthma control score, number of exacerbations, and number of hospitalizations.
 
Reported confusion matrix for change in PIF versus asthma exacerbations and poor asthma control.
	
Exploratory		

To evaluate the asthma control and health care utilization of subjects as measured by the number of exacerbations (acute worsening of asthma requiring at least 3 days of corticosteroids or a doubling dose of maintenance steroids), Emergency and hospitalization encounters, and patient-reported perceptions of asthma control.
	
 • Number of exacerbations from baseline up to one year • Number of hospitalizations • Number of emergency room visits • Mean Asthma Control Test (ACT) scores 	
Understanding the healthcare utilization and perceptions of asthma control can help researchers better understand how/whether the digihalers are helping the patients achieve better asthma control.


To determine the predictive value of inhalation parameters, including peak inspiratory flow (PIF), inspiratory time and volume, and number of inhaled doses on asthma exacerbations in a population of severe asthma patients on biologics. To determine the impact on inhalation parameters on categorical response to biologics. Response will be categorized as non-response, partial and complete response on the basis of six factors: a 50% reduction in exacerbations, any reduction in maintenance OCS dose, change of at least 10% in FEV1, improvement of 3 points in ACT score and patient
	
Algorithm that produces asthma exacerbation probability given a set of baseline and current inhalation parameters. A confusion matrix summarizing the algorithm's performance on training dataset and from which performance statistics (accuracy, sensitivity, specificity, etc.) can be computed. Proportion of patients achieving non-response, partial and complete response to biologics. Summary, chi-squared test, and Tukey's HSD test statistics of inhalation parameters by response group.
	
PIF, inspiratory time and volume are expected to vary within a patient over time; however, significant changes in these variables may indicate the development of acute exacerbations of asthma during the early phase when interventions may help change the progression of these events. Response to biologics is heterogeneous, and it is unclear if inhalational parameters measured by the Digihaler™ are

OBJECTIVES	ENDPOINTS	JUSTIFICATION FOR ENDPOINTS

perception of global improvement in asthma.
		
correlated with degree of response.


To employ machine learning techniques to a robust well characterized cohort with clinical, biological and digital markers to develop a predictive algorithm aimed at identifying responders to biologics. In addition, we would aim to develop an algorithm that can detect early changes in measured parameters that can predict long-term improvements in asthma control and exacerbations when biologics are initiated. The latter objective will be achieved by focusing on the sub-group of patients initiating biologics for the first time or switching between biologics due to perceived inadequate response.
	
Machine learning model developed for predicting responders to biologics (developed in collaboration with the University of Michigan Morphomic Analysis Group). Reporting key factors in the model that are associated with response, using inhalation parameters (digital markers), clinical factors, and biomarkers.
	
Predictive analytics have been utilized in many diseases to develop robust ways to identify response, and the use of machine learning methods has enhanced our ability to identify responders to antibiotics, predict those with a risk of poor surgical outcomes, and identify those likely to have disease progression. We will use our experience with machine learning to develop new predictive models that can help us to shift the treatment paradigm, improving our ability to make early predictions of therapeutic response in patients receiving biologics for asthma.

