5. To evaluate the asthma control and health care utilization of subjects as measured by the number of exacerbations (acute worsening of asthma requiring at least 3 days of corticosteroids or a doubling dose of maintenance steroids), Emergency and hospitalization encounters, and patient-reported perceptions of asthma control.
6. To employ machine learning techniques to a robust well characterized cohort with clinical, biological, and digital markers to develop a predictive algorithm aimed at identifying responders to biologics. In addition, we would aim to develop an algorithm that can detect early changes in measured parameters that can predict long-term improvements in asthma control and exacerbations when biologics are initiated. The latter objective will be achieved by focusing on the subgroup of patients initiating biologics for the first time or switching between biologics due to perceived inadequate response.

Endpoints:

Primary Endpoint:

Mean and median number of (daily) doses of ProAir® Digihaler™ and AirDuo® Digihaler™ utilized at baseline, temporal patterns in rescue and controller medication utilization, and within-patient parameter mean, median, and variance per-inhalation to establish baselines.

Secondary Endpoints:

1. Proportion of patients with different rates of adherence.
2. Proportion of Patients achieving non-response, partial-responses, and complete response to biologics.
3. Change in Main Peak Inspiratory volume from baseline up to one year.
4. Change in Mean Inspiratory Time from baseline up to one year.
5. Change in mean peak inspiratory flow (PIF) from baseline up to one year.
6. Change in mean forced expiratory volume in one second (FEV1) from baseline up to one year.

Exploratory Endpoints

7. Number of exacerbations from baseline up to one year.
8. Number of hospitalizations.

9. Number of emergency room visits.
10. Mean Asthma Control Test (ACT) scores.
11. Algorithm that produces a daily asthma exacerbation probability given a set of baseline and current inhalation parameters. A confusion matrix summarizing the algorithm's performance on training dataset and from which performance statistics (accuracy, sensitivity, specificity, etc.) can be computed.

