7.2 PARTICIPANT DISCONTINUATION/WITHDRAWAL FROM THE STUDY

1. Patient withdraws consent or withdrawal from the study for any reason
2. Patient experiences an adverse event or other medical condition which indicates to the investigator that continued participation is not in the best interest of the patient.
3. Patient develops an illness that would interfere with his/her continued participation.
4. Patient is noncompliant with the study procedures and assessments in the opinion of the investigator.

Patients should be treated with standard of care after withdrawal from or termination of the study as appropriate. We will obtain information on patients in the case of withdrawal from the study or discontinuation from IMP. Results of any evaluations and observations, together with a narrative describing the reason(s) for withdrawal from the study or discontinuation from IMP, must be recorded in the source documents. The case report form (CRF) must document the primary reason for withdrawal from the study or discontinuation from IMP.

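### The event counts, their regressions and the 50% exacerbation factor specify no rate, offset, window or minimum follow-up, so short observation can pass for improvement

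*Combined protocol and SAP*

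**What the plan says.** Three elements of the plan rest on numbers of events.

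- **Exploratory endpoints** (Synopsis and Section 3): "Number of exacerbations from baseline up to one year", then hospitalisations and "Number of emergency room visits". The last two carry no time window.
- **Regressions** listed in Section 3 under the secondary objective on PIF as a surrogate for FEV1: single- and multiple-predictor regressions linking inhalation parameters to "asthma outcomes such as asthma control score, number of exacerbations, and number of hospitalizations". Section 9.4.3 does not describe these regressions further and names no model for counts. Emergency room visits have no named analysis.
- **Response category** (Synopsis and Section 3): its factors include "a 50% reduction in exacerbations, any reduction in maintenance OCS dose". No reference period, follow-up period or annualisation is given. The category is a secondary endpoint, defines the comparison in Section 9.4.3 item 4, and is the outcome for the response model in item 5.

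On follow-up, Section 5.4 removes patients who never start the biologic or who stop it for whatever reason. Section 7.2 adds "Patient withdraws consent or withdrawal from the study for any reason", adverse events, illness and noncompliance, and Section 7.3 adds loss to follow-up. Section 9.4.6 places a first analysis when half the population has six months. The schedule in Section 1.3 marks exacerbations and healthcare use up to week 48 and leaves the week 52 contact blank. Section 9.3 sets no minimum follow-up and no rule for patients who leave.

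Time is handled in two places in Section 9.4.3. Item 1 offers 24-, 48- and 72-hour logistic models and a recurrent event survival model for predicting exacerbations. Item 3 compares adherence groups on outcomes in the following month.

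**The concern.** A count means the same thing for two patients only if both were watched for the same time. Without a denominator, a patient who leaves at six months has about half the expected events of an identical patient who stays.

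The exits are unlikely to be random with respect to outcome. Inadequate response is a plausible reason for stopping a biologic, and Section 5.4 removes those patients. The group the study most needs to identify as non-responders may therefore be the group with the shortest observation, and on raw counts that pushes them towards apparent improvement. An inhalation profile that goes with leaving early would be linked to few events in the Section 3 regressions. A distorted 50% factor would feed the response category, the comparison of inhalation parameters across response groups, and the response prediction model.

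**Working it through.** The plan states no event rate, dropout rate or precision for these counts, so there is no figure of its own to reproduce on this point. Its main sizing figure concerns PIF: 1.96 × 15/√100 = 2.94, which agrees with the stated ±3 but has no bearing here.

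**Inputs from the documents.** Planned participation 12 months and recruitment 6 months (Synopsis); event collection to week 48 (Section 1.3); first analysis when half have six months (Section 9.4.6).

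**Assumptions.** A 12-month pre-study comparator (Section 8.1.2.1 records a past-year exacerbation count as history but does not name it as comparator); Poisson counts; a true rate equal to the prior-year count *k* and unchanged in the study; *T* = fraction of a year observed.

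**Step 1, expected count.** This is *kT*, so with no true change it falls by 1 − *T*: 7.7% at 48/52 weeks, 25% at 9 months, 50% at 6 months.

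**Step 2, the first analysis.** If accrual is even over 6 months, half are enrolled by month 3 and reach six months at month 9. On that date follow-up runs from 9 − 6 = 3 months to 9 − 0 = 9 months. Observation is unequal even with no dropout.

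**Step 3, the 50% factor.** Raw rule: P(X ≤ ⌊k/2⌋), X ~ Poisson(kT). Annualised rule: P(X ≤ ⌊kT/2⌋). At *T* = 0.5:

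- k = 2, raw: e⁻¹(1 + 1) = 0.736; annualised: e⁻¹ = 0.368.
- k = 4, raw: e⁻²(1 + 2 + 2) = 0.677; annualised: e⁻²(1 + 2) = 0.406.

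| Prior-year events | Raw, 12 mo | Raw, 9 mo | Raw, 6 mo | Annualised, 6 mo |
|---|---|---|---|---|
| 2 | 0.41 | 0.56 | 0.74 | 0.37 |
| 4 | 0.24 | 0.42 | 0.68 | 0.41 |
| 6 | 0.15 | 0.34 | 0.65 | 0.20 |

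**Step 4, what annualising does not do.** It removes the systematic shift in the expected count but not the chance effect of short observation or the coarseness of small counts. With 4 prior events the six-month figure is 0.41 against 0.24 at a full year. With 2 prior events and a quarter-year observed it is e⁻⁰·⁵ = 0.61. Coarseness can also work the other way: with 2 prior events and 48 weeks observed, one event annualises to 52/48 = 1.08, which just misses the threshold of 1, and the probability is e⁻¹·⁸⁵ = 0.16.

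**Step 5, the regressions.** Take two groups of 50 with the same true rate of 2 per year, one seen for a full year and the other for a mean fraction *f*. The expected raw ratio is *f*. The log ratio has standard error √(1/100 + 1/(100f)). For f = 0.90 this is 0.145, and ln 0.90 = −0.105, so the shift is 0.73 standard errors. Simulation (20,000 runs, two-sided 0.05) gives false-positive rates of about 11%, 47% and 98% for f = 0.90, 0.75 and 0.50. With a log(time) offset the rate is about 5% throughout. At f = 0.90 the raw figure is 8% with a rate of 1 per year and 14% with 3. A mean of 0.90 corresponds to 20% leaving evenly over the year: 1 − 0.20/2.

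**The case against.** The best reply is that the plan is silent here and does not commit to raw counts. That stands in part. No model is named, so an analyst could still add an offset. But the endpoints are worded as numbers of events, and carrying them out as written gives the distortion shown.

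Several stronger readings are tempting, and the documents do not support them.

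- *No exacerbation analysis allows for time.* Section 9.4.3 items 1 and 3 do, through the event-time and short-horizon models and the one-month window.
- *A six-month count is set against a full prior year.* The plan defines no comparator; the past-year count is only a history item. The probabilities in the table depend on that assumption.
- *Early leavers will be scored as responders.* The 50% reduction is one of several factors and no combining rule is given, so meeting it alone does not make a responder. If removed patients are left out of the analysis, the problem becomes selection; the plan does not say which applies.
- *Early leavers necessarily have too few recorded events.* Sections 4.2 and 9.4.1 draw clinical and exacerbation data from the medical record, and Section 7.2 promises some information after withdrawal. Capture may continue for some, but its duration and use are unspecified and withdrawn consent may end it.
- *Associations will reverse in sign.* This is possible if leavers are sicker, but no calculation from the documents shows it.

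It is also fair to say that the three count endpoints are exploratory, and that 0.41 with 2 prior events arises from chance alone under complete follow-up.

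**Conclusion.** The point holds for the three exploratory counts, the Section 3 regressions on exacerbations and "number of hospitalizations", and the factor requiring "a 50% reduction in exacerbations". As written, these make no allowance for time observed in a study where exit rules and the timing of the first analysis make observation unequal. The proportional fall in expected count needs only an unchanged event rate. The probabilities of meeting the 50% factor rest on an assumed 12-month comparator, Poisson counts and illustrative prior counts of 2, 4 and 6; overdispersion would change them but not the proportional shift. That the distortion falls mostly on poor responders is likely given Section 5.4, but the documents give no frequency of stopping, so the effect on the study as a whole cannot be sized. The plan should be changed before any analysis, chiefly because the response category drives secondary comparisons.

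**What to change.** - Derive time at risk for each patient, with start, end and any medical-record capture after exit defined in advance.
- Model exacerbations, hospitalisations and emergency room visits with a negative binomial model, or Poisson with robust errors, with log(time at risk) as offset. Report events per patient-year. Hospitalisations may be too sparse with 100 patients for more than a rate and interval.
- Define the 50% factor on annualised rates against a stated reference window, and class it as not assessable below a pre-specified minimum follow-up. Reconcile collection to week 48 with the one-year endpoint, so that completers are compared over equal windows and the rounding problem in Step 4 does not arise for them.
- State whether patients removed under Section 5.4 are analysed, and apply the same rules to them and to the first analysis. An offset corrects for time, not for outcome-related exit, so exits should also be tabulated by reason and time.

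The cost is analysis-plan wording and a derived variable; scheduled contacts every four weeks supply the dates. The downside is that some patients become not assessable on this factor. Their number is unknown because the plan gives no dropout rate.
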